### Statistical analysis plan

The primary outcome and secondary outcomes 1-4 and 7 will follow the same analysis plan to study the difference in the distribution of time to an endpoint. First, the distributions for each of these outcomes will be evaluated to determine if the distribution is normal or non-parametric. If the distribution is normal, that outcome will be analyzed using a two-tailed unpaired t-test. If the distribution is non-parametric, that outcome will be analyzed using a Wilcoxon rank sum test. We expect length of stay data to follow a non-parametric distribution. In secondary outcome 2, the outcome measured is the time at which all of the necessary criteria are hit for the first time simultaneously, which accounts for the transient nature of some of these measures.

Secondary outcomes 5-6 will measure the prevalence of each of these outcomes. Prevalence was chosen over incidence in order to account for multiple instances of rebound hyperglycemia or hypoglycemia occurring within the specified timeframe for each and also the amount of time it takes to clinically reverse these conditions. For both of these outcomes, a two-proportion z test will be run to find the difference in the amount of time each treatment arm cumulatively spent with the specified condition. Finally, for the outcomes relying on certain lab values, we will examine time from IV insulin infusion start to outcome labs in both groups. If there is significant variability between the experimental and SOC arms, we will adjust for this statistically. Group randomization should ensure that variability is

equally distributed between groups, however, there is a chance of bias (e.g., if the experimental group fares better and thus are slower to get nursing checks.)

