## Study aims

Primary Outcome:

- 1) Does early administration of insulin glargine result in a shorter ICU length of stay when compared to usual care for the treatment of diabetic ketoacidosis?

Hypothesis: Early administration of insulin glargine will result in shorter ICU length of stay when compared to usual care in patients with DKA.

Secondary Outcomes:

- 1) Does early administration of insulin glargine result in a shorter hospital length of stay (defined as time between start of insulin infusion and discharge from hospital) when compared to usual care for the treatment of diabetic ketoacidosis?

Hypothesis: Early administration of insulin glargine will result in shorter hospital length of stay when compared to usual care in patients with DKA.

- 2) Does early administration of insulin glargine result in a faster recovery from DKA (defined as blood glucose < 200 and two of: Anion Gap  $\leq$  12, Serum Bicarbonate  $\geq$  15 mEq/L, or pH > 7.3) when compared to usual care for the treatment of diabetic ketoacidosis?

Hypothesis: Early administration of insulin glargine will result in a faster recovery from DKA (defined as blood glucose <200 and two of: Anion Gap  $\leq$  12, Serum Bicarbonate  $\geq$  15 mEq/L, or pH > 7.3) when compared to usual care for the treatment of diabetic ketoacidosis.

- 3) Does early administration of insulin glargine result in a shorter duration of elevated anion gap (defined as time with anion gap > 12) when compared to usual care for the treatment of diabetic ketoacidosis?

Hypothesis: Early administration of insulin glargine will result in a shorter duration of elevated anion gap (defined as time with anion gap > 12) when compared to usual care for the treatment of diabetic ketoacidosis.

- 4) Does early administration of insulin glargine result in a shorter duration of time on IV insulin infusion when compared to usual care for the treatment of diabetic ketoacidosis?

Hypothesis: Early administration of insulin glargine will result in a shorter duration of time on IV insulin infusion when compared to usual care for the treatment of diabetic ketoacidosis.

- 5) Does early administration of insulin glargine result in a lower prevalence of rebound hyperglycemia, defined as blood glucose > 180 mg/dL in the 24 hours after IV insulin infusion discontinuation, when compared to usual care for the treatment of diabetic ketoacidosis?

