### Sample size

From 1/1/2018 to 6/30/2019 there were 399 unique encounters of patients admitted to Regions Hospital with an associated ICD-10 code of E10.10 (Type 1 diabetes mellitus with ketoacidosis without coma), E10.11 (Type 1 diabetes mellitus with ketoacidosis with coma), E11.10 (Type 2 diabetes mellitus with ketoacidosis without coma),

E11.11 (Type 2 diabetes mellitus with ketoacidosis with coma), E13.10 (Other specified diabetes mellitus with ketoacidosis without coma), or E13.11 (Other specified diabetes mellitus with ketoacidosis with coma).

We expect patients to present at the same rate, indicating that an estimated 264 patients with one of these eligible diagnoses will present over the twelve months of study enrollment. Of those 264, we expect 25% to be ineligible due to meeting one of the study exclusion criteria and another 25% to be eligible but decline participation. Therefore, we expect to see 132 total eligible subjects (66 in each randomization arm). Due to our fixed sample-size, in lieu of a traditional power analysis to determine the number of subjects needed to detect a difference between the group we plugged our fixed sample size into a power analysis and solved for length of stay.

We ran a power analysis using the same historical data used under the Sample size section of this proposal. Because we expect about 132 patients to be enrolled, we inspected length of stay (LOS) from the first 100 cases in our historical data. LOS is heavily right-skewed, so we log-transformed it to estimate detectable effect size. We used the “proc power” program in SAS 9.4, which has specifications for comparing two log-transformed means. In order to achieve 80% power to detect a true difference between two fixed groups of  $n=66$ , the ratio of logs would have to be about 1.31; when normalized, this translates to about 6.5 hours ( $\alpha = 0.05$ , coefficient of variation = 0.6). So, with our sample size, we estimate that the intervention would need to cause a 6.5-hour difference in average length of stay between groups in order for us to detect a difference 80% of the time.

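### The primary test is left to an unspecified normality check, and the stated 80% power belongs to a log-scale comparison that neither branch performs; for length of stay this costs about 2-3 points of power

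*Combined protocol and SAP*

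**What the plan says.** The primary hypothesis, under Study aims, is that "Early administration of insulin glargine will result in shorter ICU length of stay when compared to usual care in patients with DKA".

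The Statistical analysis plan gives one rule for the primary outcome and secondary outcomes 1-4 and 7: "the distributions for each of these outcomes will be evaluated to determine if the distribution is normal or non-parametric". If the answer is normal, "that outcome will be analyzed using a two-tailed unpaired t-test". Otherwise, "that outcome will be analyzed using a Wilcoxon rank sum test". It adds: "We expect length of stay data to follow a non-parametric distribution". It does not name a normality test or threshold, or say whether the check is pooled or by arm. It mentions no transformation, and it names no effect estimate or confidence interval for either branch.

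The Sample size section states: "LOS is heavily right-skewed, so we log-transformed it to estimate detectable effect size". The calculation used a SAS procedure "which has specifications for comparing two log-transformed means". With 66 per arm, alpha 0.05 and a coefficient of variation of 0.6, it gives 80% power at a ratio of about 1.31, translated to about 6.5 hours.

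**The concern.** There are two separate problems.

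- **The test is chosen from the trial's own data by an undefined check.** The branches do not answer the same question: one compares means in hours, the other compares ranks. Allocation is known during the trial, because controls receive no placebo and the randomization list conceals only future assignments. No masking of the analysis is described. An undefined check, applied outcome by outcome, therefore leaves room for judgment after the results can be seen.
- **The power statement and the analysis do not match.** The 80% comes from a comparison of log means that the analysis section never plans. With no effect estimate specified, nothing in the planned output corresponds to the design target of 1.31.

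**Working it through.** **Inputs (Sample size section):** 66 per arm, alpha 0.05, coefficient of variation (CV) 0.6, ratio 1.31, power 80%. The section does not state sidedness. Two-sided is used here because it reproduces the figure and matches the two-tailed t-test in the analysis section.

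**Step 1. Reproduce the stated figure.** Under a lognormal model the log-scale SD is sqrt(ln(1 + 0.6²)) = sqrt(ln 1.36) = 0.5545.

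- Detectable ratio, normal approximation: exp[(1.960 + 0.842) × 0.5545 × sqrt(2/66)] = exp(2.802 × 0.5545 × 0.1741) = 1.3105.
- Detectable ratio, noncentral t: 1.313.
- Power at 1.31: 79.9% (normal approximation) or 79.3% (noncentral t).
- Alternatives that fail to reproduce it: one-sided alpha gives a ratio of 1.273, and using 0.6 directly as the log SD gives 1.340.

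The plan's figure is therefore right for a two-sided t-test on log length of stay.

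**Step 2. Power of the tests actually planned.** This used 40,000 simulated lognormal trials with 66 per arm and CV 0.6. The Monte Carlo standard error is about sqrt(0.77 × 0.23/40,000) = 0.2 points. Shapiro-Wilk at 5% stands in for the unnamed check, which is an assumption.

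| Analysis | Power at ratio 1.31 | Type I error at ratio 1.0 |
|---|---|---|
| Log-scale t-test (used for sizing, not planned) | 79.3% | 5.0% |
| Wilcoxon (expected branch) | 77.1% | 5.0% |
| t-test on raw hours (other branch) | 73.3% | 4.9% |
| Check, then choose | 77.1% | 5.0% |

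The assumed check rejects normality in more than 99.9% of these trials, so for length of stay the two-stage rule and Wilcoxon coincide.

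**Step 3. Detectable effect under Wilcoxon.** At 66 per arm, simulated power is 79.0% at a ratio of 1.32 and 80.7% at 1.325, so 80% needs slightly over 1.32. At a ratio of 1.31, power is 79.5% with 70 per arm and 80.5% with 72.

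**Step 4. Sensitivity to the CV, at ratio 1.31.**

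| CV | Log-scale t | Wilcoxon | Raw t |
|---|---|---|---|
| 0.4 | 97.9% | 97.4% | 97.0% |
| 0.6 | 79.3% | 77.1% | 73.3% |
| 0.8 | 59.7% | 57.2% | 50.1% |

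Uncertainty about the CV moves power far more than the choice between log-scale t and Wilcoxon.

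**Step 5. Is the log-scale t-test clearly better?** The log SD was kept at 0.5545 and the ratio at 1.31, and log length of stay was allowed to depart from normal (assumed shapes). With a t distribution on 5 df, power is about 80% for log-t and 87% for Wilcoxon. With residual right skew (gamma, shape 4), it is about 79% and 84%. Wilcoxon gives up about 2 points when lognormality is exact and gains 5-7 in these two cases.

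**The case against.** The strongest defence is that the choice is nearly nominal for the primary outcome. The plan says in advance that it expects the non-parametric branch, and Step 2 bears this out. The sample size was fixed by expected accrual and the calculation was solved for the effect, so no enrolment decision rests on the difference between 1.31 and 1.32. All of this stands, and it limits the size of the point.

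Four stronger readings are tempting, and the documents do not support them:

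- **That choosing the test from the data inflates false positives.** Under the plan's own lognormal model, type I error stays near 5%.
- **That about 6 points of power are lost.** That figure (79.3% against 73.3%) applies only if heavily skewed data were declared normal and analysed in raw hours.
- **That Wilcoxon cannot yield an effect in hours or as a ratio.** Its Hodges-Lehmann companion gives a shift in hours on raw values and a ratio on log values. In simulation at the plan's inputs, the ratio centres on about 1.31 with about 95% interval coverage. The gap is that the plan names no estimate.
- **That the historical data settle every outcome.** The Sample size section says only length of stay, without specifying ICU or hospital, and does not show that its logarithm is normal. It is silent on outcomes 2, 3, 4 and 7.

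The defence does not reach the outcomes whose skew is unknown. Mean glucose (outcome 7) is a concentration rather than a duration, and nothing in the plan predicts which branch it will take.

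**Conclusion.** The point holds at modest size. The plan has no single named primary test, and its 80% power is correct for an analysis it does not include. For length of stay the rule is in effect Wilcoxon, with about 77% power at a ratio of 1.31. That is about 2 points below the log-scale t-test and 3 below the nominal 80%. There is no sign of type I inflation. For less skewed outcomes the branch is open and would be chosen with the data in view in an open-label trial.

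A reader might infer that the log-scale t-test is the only correct primary analysis. That does not follow: it matches the power calculation, but its advantage depends on lognormality that the plan has not shown.

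The figures assume lognormal length of stay with equal CV in both arms, that the historical CV applies to ICU stay, and Shapiro-Wilk at 5% as the check. The change is worth making because it costs almost nothing, removes the weaker raw-scale branch and closes the discretion.

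**What to change.** Delete the normality step and name one test per outcome in advance.

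- **Length of stay (primary outcome and secondary outcome 1), one of two options.** (a) Wilcoxon, with a Hodges-Lehmann estimate and 95% CI, computed on log values if a ratio is wanted. Restate power as about 77% at 1.31, or the detectable ratio as about 1.32. (b) A t-test or linear model on log values, reported as a geometric mean ratio with 95% CI. This keeps the stated 80%, with Wilcoxon as a fixed sensitivity analysis. A linear model could also carry covariates, which the planned two-sample tests cannot.
- **Durations that can be zero.** Entry needs an anion gap above 10, while outcome 3 counts time above 12, so some patients may contribute zero. Use Wilcoxon there rather than a logarithm with an arbitrary offset.
- **Remaining outcomes, including mean glucose.** State one test and its effect estimate for each, and describe outcome 7 as a concentration rather than a time to an endpoint.

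The cost is one paragraph of SAP text and no new data. The downside is a slightly less favourable power figure if Wilcoxon is kept, or reliance on approximate lognormality if the log-scale analysis is chosen.

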### Variable list, sources, and data collection

The variables listed on the below data collection form will be incorporated into a secure REDCap database that research staff will use to enter the data. Patients will be assigned study ID numbers in the REDCap database. The REDCap database will contain identifying information, however, if de-identified data needs to be shared outside of the direct study team, the dataset can be downloaded without identifying variables such as MRN.

Variable Name	Role of Variable	Measurement Scale
Study ID	Unique identifier	Continuous (001 – n)
MRN	Link to EMR	String
Full name	Link to EMR	String
Date of ED presentation	Link to EMR	DMY
Age	Descriptive	Continuous
Race	Descriptive	Categorical, as reported in Epic
Ethnicity	Descriptive	Categorical, as reported in Epic
Sex at birth	Descriptive	Categorical, as reported in Epic
End stage renal disease or hepatic disease	Inclusion/exclusion criteria	Binary
Vasopressor dose to treat hypotension at any point during admission	Inclusion/exclusion criteria	Binary
On insulin pump therapy at baseline (prior to ED)	Inclusion/exclusion criteria	Binary
On combination insulin products (i.e. Novolin® 70/30, Novolog® 70/30, Humalog® 75/25, etc.) at baseline	Inclusion/exclusion criteria	Binary
Presenting pH (prior to intervention)	Inclusion/exclusion criteria	Continuous

Time of first pH	Calculate time to resolution	Continuous
Time of short-acting insulin start	Calculate time to resolution	Continuous
Time of first pH > 7.3	Outcome Calculate time to resolution	Continuous
Presenting blood glucose in mg/dL	Inclusion/exclusion criteria	Continuous
Time of first blood glucose < 250 mg/dL	Outcome Calculate time to resolution	Continuous
Blood glucose > 180 mg/dL in the 24 hours after IV insulin infusion discontinuation	Outcome	Binary
Blood glucose < 70mg/dL $\geq$ 1 time at any point while on IV insulin therapy or in the 24 hours after IV insulin infusion discontinuation	Outcome Prevalence of AE (hypoglycemia)	Binary
Blood glucose < 70mg/dL at any point between glargine start and 24 hours after IV insulin infusion discontinuation (control group only)	Outcome Prevalence of AE that may be contributable to study intervention (hypoglycemia)	Binary
Mean blood glucose in 24 and 48 hours after IV insulin infusion discontinuation	Outcome	Continuous
Presenting anion gap	Inclusion/exclusion criteria	Continuous
Time of first anion gap	Calculate time to resolution	Continuous

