Time of first anion gap < 12	Calculate time to resolution	Continuous
Presenting serum bicarbonate level in mEq/L	Inclusion/exclusion criteria	Continuous
Time of first serum bicarbonate < 15 mEq/L	Calculate time to resolution	Continuous
Presence of ketonuria or ketonemia on presentation	Inclusion/exclusion criteria	Binary
Presenting Beta-Hydroxybutyrate in mmol/L	Inclusion/exclusion criteria	Continuous

Type I or Type II Diabetes	Descriptive	Binary
Prior to admission history of current basal insulin usage	Treatment determination if in intervention arm	Binary
Home Insulin Dose	Treatment determination if in intervention arm	Continuous
Time of IV insulin infusion initiation	Ensure protocol compliance Start of outcome measure	Date/Time
Time of IV insulin infusion discontinuation	Outcome	Date/Time
Time of SC insulin glargine administration	Descriptive Ensure protocol compliance	Date/Time
Exact dose of SC insulin glargine administered	Descriptive Ensure protocol compliance	Date/Time
Weight in kg	Determine insulin glargine dose for study order	Continuous
Date/time of ICU admission	Calculate ICU LOS post-infusion for study outcome	Date/time
Date/time of ICU discharge (defined as time of service switch to progressive care or general medicine)	Calculate ICU LOS post-infusion for outcome	Date/time
Date/time of IV insulin infusion start	Calculate LOS post-infusion for study outcome	Date/time
Date/time of hospital discharge	Calculate LOS for study outcome	Date/time

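### The primary test of ICU length of stay ignores baseline severity that is already recorded; a pre-specified, covariate-adjusted rank analysis would probably gain precision, by an amount the documents cannot fix

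*Combined protocol and SAP*

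**What the plan says.** Under Statistical analysis plan, the primary outcome and secondary outcomes 1-4 and 7 share one approach. Each distribution is inspected. If it is normal, the test is a "two-tailed unpaired t-test"; otherwise, "If the distribution is non-parametric, that outcome will be analyzed using a Wilcoxon rank sum test". The authors expect the second case for length of stay. No baseline covariate is named for any outcome. The only adjustment, there and under Strengths and limitations, is a conditional one for the timing of outcome labs, which does not bear on ICU stay.

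The Variable list records presenting pH, glucose, anion gap and bicarbonate (for example "Presenting serum bicarbonate level in mEq/L") and age as continuous variables, and diabetes type as binary. Their stated roles are eligibility or description only. Under Screening, a patient with any qualifying lab missing is not eligible. Randomization describes a single list of 150 with 75 per arm and no stratification.

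The Sample size section takes enrollment as given (66 per arm) and solves for the detectable difference on the log scale: "LOS is heavily right-skewed, so we log-transformed it to estimate detectable effect size". The result for 80% power is that "the ratio of logs would have to be about 1.31", at a two-group alpha of 0.05 and a coefficient of variation of 0.6.

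**The concern.** When the number of patients is set by accrual, explaining outcome variance is one of the few remaining ways to gain precision. The presenting labs are plausible candidates on the documents' own terms. Under Background, an anion gap limit and a pH limit are among the hospital's conditions for leaving IV insulin. Secondary outcomes 2 and 3 are times until these same quantities cross a threshold, so the presenting values are their starting levels. The labs are complete by eligibility, so using them loses no patients. Neither the randomization nor the analysis uses them. What is at stake is efficiency, and with it the chance of missing a real effect of the size the plan was built around.

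**Working it through.** **1. Reproduce the planning figure.** Inputs from Sample size: n = 66 per arm, alpha 0.05, power 80%, CV 0.6. Two-sidedness comes from the Statistical analysis plan. The 1.31 is read as a ratio of geometric means.

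- Log-scale SD = √ln(1 + 0.6²) = √ln 1.36 = 0.5545.
- Standard error of the difference = 0.5545 × √(2/66) = 0.0965.
- Detectable ratio = exp[(1.960 + 0.842) × 0.0965] = 1.311; with the noncentral t it is 1.313.
- Power at 1.31: ln 1.31 = 0.270, 0.270/0.0965 = 2.80, and Φ(2.80 − 1.96) = 79.9% (t version 79.3%).

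The plan's figure reproduces, but it belongs to an unadjusted t-test on logs. On the same lognormal inputs the Wilcoxon test that the plan expects to use has about 77% power in simulation.

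**2. Formula for the gain.** Let R² be the share of log-stay variance explained by the covariates. **The documents give no value; 0 to 0.30 is an assumption.** The residual SD becomes 0.5545 × √(1 − R²), and the equivalent unadjusted total is 132/(1 − R²). For R² = 0.05, 0.10, 0.20 and 0.30 the power is 81.9%, 83.9%, 87.9% and 91.7%, and the equivalent total is 139, 147, 165 and 189. These figures leave out the cost of estimating the covariate effects and compare with a log t-test, so they are a ceiling.

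**3. Simulation with normal log stay** (66 per arm, ratio 1.31, four covariates; power in %). The rank-adjusted values rest on 4,000 trials each, so their Monte Carlo standard error is about √(0.8 × 0.2/4000) = 0.6 points.

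| R² | Wilcoxon | log t-test | log-scale model, adjusted | rank analysis, adjusted |
|---|---|---|---|---|
| 0 | 77.2 | 79.5 | 78.4 | up to about 2 points lost |
| 0.05 | 76.5 | 78.9 | 79.6 | about level with Wilcoxon |
| 0.10 | 77.3 | 79.4 | 82.0 | 81 |
| 0.20 | 77.1 | 79.1 | 86.5 | 84 |
| 0.30 | 76.5 | 78.7 | 90.1 | 88 |

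With five covariates the adjusted log-scale model gives 76.9, 79.3, 82.3, 85.3 and 89.8. Its gain over Wilcoxon is thus about 3 points at R² = 0.05 and 13 at 0.30. Against the log t-test it breaks even near R² = 0.04.

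**4. Simulation with heavy-tailed log stay** (t residuals with 4 df, an assumption; same log SD; ratio 1.31 or 1.313; ranges cover two sets of runs).

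| R² | Wilcoxon | log-scale model, adjusted | rank analysis, adjusted |
|---|---|---|---|
| 0 | 91 | 80 | not tabulated |
| 0.05 | 89-90 | 81-83 | not tabulated |
| 0.10 | 87-88 | 83 | 90 |
| 0.20 | 85-86 | 87 | 93 |
| 0.30 | 85 | not tabulated | 95 |

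The choice of model therefore matters as much as the choice to adjust. The log-scale model loses to Wilcoxon by 7 to 8 points at R² = 0.05 under heavy tails. The adjusted rank analysis is ahead of Wilcoxon from R² = 0.10 upward under both shapes.

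**The case against.** The strongest reply is that the planned test is valid and that the gain rests wholly on an R² nobody has supplied. That stands. The value may also be modest: pH, bicarbonate and anion gap are truncated by the eligibility limits and probably overlap, ICU discharge is recorded as a change of service, and leaving IV insulin also depends on stable glucose, vital signs and electrolytes and on eating.

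A second reply is that moving to a linear model on logs can lose power. That also stands. The Sample size section says only that stay is right-skewed, not that its logarithm is normal. Nor can logs be taken of a zero: a patient may qualify with an anion gap just above 10, while outcome 3 counts time above 12, so some durations may be zero. These points decide the form of the adjustment, not whether to adjust.

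A third reply is that the sample is not rigidly fixed, since the list allows 150. At 75 per arm the standard error is 0.5545 × √(2/75) = 0.0905, and power is Φ(0.270/0.0905 − 1.96), about 85%. That is true if enrollment exceeds expectation, but it cannot be planned on.

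A reader might also infer that a chance imbalance in severity biases the unadjusted comparison. It does not: under randomization the test's error rate already allows for such imbalance.

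**Conclusion.** The point holds as a missed gain in efficiency, not as an error in the planned test. The primary analysis is unadjusted, the covariates are on the form, and the qualifying labs are complete by design. For an assumed R² of 0.05 to 0.30, rank adjustment adds roughly 0 to 10 points of power over Wilcoxon. A log-scale model would add about 3 to 13 points if log stay is normal, but can lose power if it is heavy-tailed. If the covariates are not prognostic, the cost is a few degrees of freedom and up to about 2 points.

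Two stronger readings are not supported. One is that the power is there for the taking at no risk; without an R² in the documents, the gain is likely but not assured. The other is that it can be stated in hours of ICU stay. The plan says that its ratio means "this translates to about 6.5 hours", but the Sample size section does not say whether the underlying stay is ICU or hospital, so no conversion is made here.

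**What to change.** In the Statistical analysis plan, before outcome data are examined:

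- Name as primary a covariate-adjusted rank analysis of ICU length of stay (rank ANCOVA or a proportional-odds model; choose one) with arm, presenting pH, presenting anion gap, age and diabetes type, two-sided at 0.05. A plain Wilcoxon test cannot take covariates; these methods can, and they keep its robustness and accept zero durations.
- Report the unadjusted Wilcoxon test as a sensitivity analysis.
- For length of stay, add a log-scale linear model with the same covariates as a supportive estimate, giving the adjusted ratio of geometric means with its 95% confidence interval.
- Use the same covariates for secondary outcomes 1-4 and 7, adding presenting glucose for outcomes 2 and 7.
- State how diabetes other than type I or II is coded. The form is binary, while the planning codes include other specified diabetes.

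The cost is SAP wording, one coding rule and four covariate degrees of freedom (five where glucose is added). No new data are needed.
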